- 5. English speaking and able to give informed consent
- 6. Willing and able to complete all study questionnaires
- 7. Ambulatory

Exclusion Criteria

- 1. Prior sacrospinous ligament fixation procedure.
- 2. Any serious disease or chronic condition that could interfere with the study compliance
- 3. Inability to give informed consent
- 4. Pregnancy or planning pregnancy prior to the 6 week postoperative visit
- 5. Prior pelvic radiation
- 6. Incarcerated

- 7. Prior augmented (synthetic mesh, autologous graft, xenograft, allograft) prolapse repair
- 8. History of significant buttock or leg pain in the past 3 months
- 9. History of fibromyalgia, polymyositis, dermatomyositis, systemic lupus erythematosus, or other auto-immune myalgic conditions
- 10. Current regular narcotic drug therapy for any chronic pain condition
- 11. History of loss of motor or sensory function of the lower extremities
- 12. History of sacral decubitus ulcers
- 13. Planned concomitant levatorplasty; anal sphincteroplasty, anal fissurectomy, rectopexy, or hemorrhoidectomy

STUDY POPULATION, RECRUITMENT AND SCREENING

Study population participants will consist of women who are scheduled to undergo native tissue POP repair using apical support to the sacrospinous ligament. Women scheduled to undergo sacrospinous hysteropexy and sacrospinous suspension of the vaginal vault will be recruited at Wake Forest Baptist Medical Center.

Participants must have vaginal bulge symptoms defined by positive responses to a validated instrument, the Pelvic Floor Distress Inventory (PFDI)^{14,15}, Stage II or greater POP in any vaginal compartment as determined by the Pelvic Organ Prolapse Quantification (POPQ) system,¹⁶ a validated tool designed to assess the degree of vaginal prolapse, and an apical prolapse contribution to the patient's overall pelvic organ prolapse as deemed by the examining physician. An apical prolapse contribution is detected by either the descent of the "C" component of the POP-Q system or as the demonstration of at least partial correction of an anterior or posterior prolapse via manipulated suspension of the apex during on pelvic examination.

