Study subjects will be recruited from patients who present to the Urology or Gynecology clinical sites at Wake Forest Baptist Health. Institutional review board (IRB) approval will be obtained at this site. There will additionally be advertisement of the study through print or digital media to assist in patient recruitment. All advertisements will abide by research study advertisement regulations set by Wake Forest Baptist Health.

Potential subjects will be identified by members of the Urology and Gynecology departments at Wake Forest Baptist Health. Eligible patients who agree to participate will be provided written informed consent administered by the collaborators listed on the IRB document.

PRE-INTERVENTION ASSESSMENTS

All women presenting to the participating clinical center with signs and symptoms of prolapse who have elected to undergo sacrospinous ligament suspension will be screened for their eligibility. If eligible and consenting, the following baseline data will be collected on paper forms that will then be transcribed into a secure REDCap (Research Electronic Data Capture) database:

- 1. Demographic data including age, race, BMI, insurance status, level of education obtained
- 2. Pre-operative morbidity as measured using the Charlson Comorbidity Index
- 3. Smoking status
- 4. POP-Q data
- 5. Need for ambulation assistance
- 6. History of lower extremity disease, injuries, and functionality
- 7. Medical and surgical history
- 8. Level of pre-operative pelvic pain using 10-point NRS
- 9. PFDI questionnaire

RANDOMIZATION AND MASKING

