This trial has a **primary** outcome of level of postoperative buttock or posterior thigh pain on postoperative day 1, week1, and 6 weeks as measured using the NRS. An independent t-test will be used to compare the means of the NRS scores from the two groups. The NRS is one of the most common validated pain questionnaire modalities.^{17,18,19,20,21} A clinically significant difference will be considered 2.5 on the 10-point NRS based on a prior paper assessing buttock pain from sacrospinous ligament fixation²² and with published studies assessing clinically meaningful decreases in acute pain.^{18,17} The patient's will be given copies of the NRS questionnaire which will be collected in person on postoperative day 1, week 1, and 6 weeks postoperatively.

Secondary outcome measures will assess the degree to which the study intervention influences surgeon satisfaction, surgical efficiency, adverse events intra- and postoperatively, surgical success, symptomatic success, and the level of postoperative general pelvic pain. Surgeon satisfaction will be assessed via a 5-point rating scale (very dissatisfied, somewhat dissatisfied, neutral, satisfied, very satisfied) and treated as categorical values. Surgical efficiency will be assessed as continuous data measured as a means in minutes. Adverse events will be evaluated as dichotomous data. All adverse events will be reported by the Dindo classification system. Short-term objective surgical success will be assessed by a postoperative exam at 6 weeks and descent of the vaginal apex beyond TVL/2 will be considered surgical failure. Symptomatic success will be assessed by the PDFI-20 guestionnaires to be given at 6-weeks post-operation and compared to preoperative values. The patient's will also be queried about their general pelvic pain on the same questionnaires used to assess buttock and posterior thigh pain. Oral opioid use following hospitalization until postoperation day 6 will be recorded via opioid use questions on the 1 week postoperation guestionnaire. The opioid dose will be converted into morphine equivalents for data analysis. Statistical analysis will be done in collaboration with the Wake Forest Baptist Hospital CTSI Biostatistics Department. Independent t-tests will be used for all continuous data, except for the PFDI and PFIQ data that will use paired t-tests as the two samples are dependent. Chi-square tests will be used for all dichotomous and categorical data.

POWER CALCULATION:

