This study is a head to head two sample comparative study. The null hypothesis is that there is no difference in the prevalence of immediate postoperative new buttock or posterior thigh pain with the use of the Anchorsure® System compared to the Capio[™] Slim device for sacrospinous ligament fixation. In prior published study by Ferrando et al the mean postoperative day 1 buttock or posterior thigh pain had a greater standard deviation (2.7-2.9) compared to week

1 and week 6 data. Therefore for our power calculation used an expected standard deviation of 2.9 to provide confidence in our power of assessing the difference in pain scores across all three timepoints.²² A decrease in in-hospital postoperative buttock or posterior thigh pain prevalence of 2.5 on a 10-point scale was chosen as clinically significant and is consistent with published data.^{22,18,17} Using a standard deviation of 2.9 and a difference in pain scores of 2.5 setting the level of significance, 21 patients are required in each group to provide a power of at least 80% to reject the null hypothesis (H0) that the Anchorsure® System does not lead to significantly less postoperative buttock and posterior thigh pain than does the Capio[™] Slim Device in favor of the alternate hypothesis that the Anchorsure® System leads to significantly less postoperative pain than the Capio[™] Slim Device using a two-sample normal approximation test of means with a two-sided 5% significance level. Assuming a 15% loss to follow-up or drop-out rate for the duration of the study, the total enrollment goal is 48 patients (24 in each group). The null hypothesis will be declared rejected if the mean of immediate postoperative buttock and posterior thigh pain with use of the Anchorsure® device is less from the mean with the use of the Capio[™] Slim device with a p-value of 0.05 or less. The power calculations and their adjustment from the original study goal of 60 recruited patients (using 90% power and a standard deviation of 3) were confirmed with the Wake Forest Baptist Hospital CTSI Biostatistics Department.

Form / Intervention	Preop Clinic	Intra- operatively	Day 1	Week 1	Week 6
Informed Consent	Х				
Study Inclusion Form	Х				
Preop Baseline Data Form with					
Charlson Comorbidity Index and	Х				
POP-Q					
PFDI-20 and PFIQ-7 Forms	Х				Х
NRS Pain Questionnaires	Х		Х	Х	Х
Oral Opioid Use Questionnaire				Х	
Randomization		Х			
Adverse events		Х	Х	Х	Х
Surgeon Questionnaire		Х			

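### A pre-operative NRS is collected but no pain comparison uses it; adjusting for one baseline item may add precision, mainly for general pelvic pain

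*Combined protocol and SAP*

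**What the plan says.** - **Analysis.** Clinical outcomes prescribes for the primary outcome: "An independent t-test will be used to compare the means of the NRS scores from the two groups". For the rest it says: "Independent t-tests will be used for all continuous data, except for the PFDI and PFIQ data that will use paired t-tests". General pelvic pain on the NRS therefore also gets an unadjusted comparison. No regression model or covariate appears in the document.
- **Baseline collection.** Item 8 of the baseline list under Pre-intervention assessments is: "Level of pre-operative pelvic pain using 10-point NRS". It names no buttock or thigh item. The Calendar of Events has a row, "NRS Pain Questionnaires", marked at the pre-operative clinic, day 1, week 1 and week 6.
- **Content of the form.** Clinical outcomes says that patients will be "queried about their general pelvic pain on the same questionnaires used to assess buttock and posterior thigh pain".
- **Eligibility.** Exclusion criterion 8 is: "History of significant buttock or leg pain in the past 3 months".
- **Hypothesis.** The Power calculation section states the null as "no difference in the prevalence of immediate postoperative new buttock or posterior thigh pain".

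**The concern.** The trial is small, and the patients expected to complete it number slightly fewer than the sample size calculation asks for. A baseline measure of pain that predicts post-operative pain would remove some of the residual variance at almost no cost, but only if the adjustment is pre-specified. As written, the pre-operative score is collected and then left out of every comparison.

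The case is clearest for general pelvic pain. Its baseline is the same item on the same scale, it is expressly collected, and exclusion 8 does not screen it out. For buttock and posterior thigh pain the position is less clear, because the baseline list does not say that this item is recorded before surgery.

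**Working it through.** **Inputs.** From Power calculation: difference 2.5, SD 2.9, 24 enrolled per group, 15% drop-out, and a "two-sample normal approximation test of means with a two-sided 5% significance level". Completers per arm: 24 × 0.85 = 20.4. The correlation r between the baseline item and the post-operative score is not in the documents. It is assumed, over the range 0 to 0.5.

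**The plan's own figure.** n per group = 2 × [2.9 × (1.960 + 0.842) / 2.5]² = 21.1, which rounds up to 22, against 21 stated. Normal-approximation power at 21 is 79.8%. The stated figure reproduces to within one patient.

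**Plain t-test at 20.4 per arm.** SE = 2.9 × √(2/20.4) = 0.908. Noncentrality = 2.5/0.908 = 2.753, with 2 × 20.4 − 2 = 38.8 df. Two-sided 5% power = 76.6%.

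**One baseline covariate.** Two things change:

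1. The residual variance is multiplied by (1 − r²).
2. Estimating the covariate's slope costs one df (37.8 left) and inflates the expected variance by 1 + 1/(2n − 4) = 1 + 1/36.8 = 1.027.

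So SE = 0.908 × √[(1 − r²) × 1.027].

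| Assumed r | Variance relative to t-test | SE | Power |
|---|---|---|---|
| t-test, no covariate | 1 | 0.908 | 76.6% |
| 0 | 1.027 | 0.920 | 75.4% |
| 0.2 | 0.96 × 1.027 = 0.986 | 0.902 | 77.1% |
| 0.3 | 0.91 × 1.027 = 0.935 | 0.878 | 79.2% |
| 0.5 | 0.75 × 1.027 = 0.770 | 0.797 | 86.4% |

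**Break-even.** The expected SE falls only if (1 − r²) × 1.027 < 1, that is, if |r| exceeds about 0.16.

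**Why one covariate and not two.** With both NRS items in the model the variance factor is 1 + 2/(2n − 5) = 1 + 2/35.8 = 1.056, on 36.8 df. Power is then 74.2, 75.9, 78.1 and 85.4% at a multiple correlation of 0, 0.2, 0.3 and 0.5. At 0.2 that is below the plain t-test.

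**Scope.** The power column uses the SD and difference given for buttock and thigh pain. The plan claims no power for general pelvic pain. For that outcome only the relative-variance column carries over, because it does not depend on the SD.

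**The case against.** The strongest objection is that the gain is unproven for the primary outcome. Exclusion 8 removes significant buttock or leg pain, and exclusions 9 to 11 remove myalgic conditions, regular narcotic use for chronic pain and lower-limb motor or sensory loss. Baseline buttock and thigh scores should therefore lie near zero with little spread. The Background attributes the post-operative pain to nerve entrapment at surgery, which pre-operative pain has no evident reason to predict. This stands. A correlation below 0.16 is plausible for that outcome, and adjustment would then cost a little.

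It is also true that the unadjusted test is unbiased under randomisation, that its standard error already reflects chance imbalance, and that it matches the two-sample comparison of means used for the sample size. This stands too, and it rules out calling the t-test a mistake.

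Two stronger readings are tempting:

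- A reader might infer that precision is being lost for free. The documents give no correlation, and a covariate that predicts nothing lowers power slightly.
- A reader might infer that *new* buttock pain, as the null hypothesis words it, cannot be told from mild existing pain because no such baseline is taken. That is not established. The calendar schedules the NRS questionnaires pre-operatively, and the same questionnaires are said to cover both sites, so the item may already be on the form. The form itself is not in the document. What remains is that the baseline list does not match the shared questionnaire.

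Neither point disposes of the case for general pelvic pain, or of the advantage of settling the adjustment in advance.

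**Conclusion.** The point holds as an efficiency improvement. A pre-operative NRS is collected and goes unused, and adjusting for it may gain precision. Against 76.6% for the plain t-test, one covariate changes power by −1.2 points at r = 0, +0.5 at 0.2, +2.6 at 0.3 and +9.8 at 0.5. The downside is thus about one point. In this range 80% is passed only at r = 0.5, so adjustment should not be presented as a sure way to restore the planned power.

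The size rests on the assumed r, the plan's SD and difference, and 15% drop-out. The expectation of a small gain for buttock and thigh pain and a larger one for general pelvic pain is a judgement from exclusion 8 and from the match of baseline item to outcome. The documents contain no data on it.

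**What to change.** 1. **Clinical outcomes, general pelvic pain.** At each time point, use a linear model of the post-operative NRS on arm, adjusted for the pre-operative pelvic NRS.
2. **Clinical outcomes, buttock and posterior thigh pain.** Use a linear model on arm adjusted for one pre-specified baseline NRS item: the buttock and thigh item if it is on the pre-operative questionnaire, otherwise the pelvic item. Fix the choice before any outcome data are examined.
3. **Sensitivity analysis.** Keep the unadjusted independent t-test for both outcomes.
4. **Pre-intervention assessments, item 8.** List the buttock and posterior thigh NRS alongside the pelvic NRS, so that the list agrees with the shared questionnaire.

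The cost is a sentence or two of analysis text, one line in the baseline list (and one item on the form if it is not already there), and one degree of freedom per model. No extra visit is needed, because the questionnaire is already scheduled before surgery.

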Access to the retroperitoneal space will be accomplished either via a circumferential pericervical, an anterior, or a posterior. The method of surgical approach will be recorded. Sharp and blunt dissection will be performed to gain access to the sacrospinous ligament(s). Surgeon discretion will determine if unilateral or bilateral fixation is performed for vaginal vault suspension but only unilateral sacrospinous ligament suspension will be permitted for hysteropexy. Surgeon discretion will determine the type and number of sutures or anchors to be placed through the sacrospinous ligament and this data will be recorded. All sutures and anchors placed into the sacrospinous ligament will be placed at least 2cm medial to the ischial spine. Suture(s) will be placed through any anchors with the choice of suture to be determined by the surgeon as this is not anticipated to interfere with any results. The suture(s) placed through anchors or the sacrospinous ligament directly will then be attached to the cervix and/or vaginal apex. Sacrospinous sutures will be tied down once all mid-vaginal repairs are completed. Transvaginal hysterectomy, bilateral salpingectomy, bilateral oophorectomy, and enterocele repair procedures will be performed prior to sacrospinous ligament fixation.

POST-INTERVENTION ASSESSMENTS

The primary study endpoints will be assessed on postoperative day 1, postoperative week 1, and postoperative week 6 via a NRS. Day 1 questionnaires will be given during morning rounds. 1 week following their procedure, patient's will be called at home to remind them to fill out the week 1 questionnaire that would have been given to them during their hospital stay. This questionnaire will be accompanied with a pre-paid and pre-addressed envelope for the patient to use or, if desired, they can bring the completed week 1 questionnaire to their week 6 follow up appointment. All patients will return to the clinic for 1-week and 6-week post-surgery follow up appointments and will fill out an NRS pain assessment (1-week and 6-week), opioid use questionnaire (1-week), PFDI questionnaire (6-week), physical examination including POP-Q (6-week), and review of any postoperative complications (1-week,6-week).

Clinical outcomes

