Gift Card Disbursement and Gift	T				Х
Card Confirmation Form					
Completion of Study Form					Х

CALENDAR OF EVENTS

DATA COLLECTION & MANAGEMENT

Data collection will occur in the clinic and in the hospital at each encounter outlined in the Calendar of Events. All study data will be recorded on data collection sheets and will be transcribed into REDCap. Any discrepancies between progress notes and supporting source documents such as physician's notes should be explained in the progress notes. Any changes made to original written entries in progress notes should be crossed through with a single line, initialed, and dated by the person making the correction to not obscure the original entry. Any changes made to original electronic entries in progress notes should be implemented in an electronic note addendum that is signed and dated by the person making the correction to not obscure the original entry.

Data will be entered by study staff into a REDCap database (described in detail in the "STUDY SUBJECT PROTECTION" section of this protocol) that will be stored on a secure server by the data coordinating center. Study data source documentation and progress notes will be monitored by the data coordinating center as outlined in the "STUDY MONITORING AND DOCUMENTATION" section. Data collected from visits should be entered into REDCap within 5 business days. Any queries to data entered into REDCap should be addressed within 5 business days. The study coordinators will regularly check REDCap for queries.

The study site will maintain all essential study documents in original format and source documentation that support the data collected on study participants in compliance with ICH/GCP guidelines. Documents must be retained until at least 2 years have elapsed since the formal discontinuation of the clinical investigation. The study site will be responsible to ensure that these essential documents are retained and are not accidentally damaged or destroyed prior to the required elapsed time.

STUDY MONITORING AND DOCUMENTATION

Study Monitoring

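### Week-6 pain, symptom and complication data are collected only at the clinic visit, although all but the POP-Q could be obtained by phone or mail from a patient who does not attend

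*Combined protocol and SAP*

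**What the plan says.** The Clinical outcomes section describes the NRS questionnaires as ones "which will be collected in person on postoperative day 1, week 1, and 6 weeks postoperatively". Post-Intervention Assessments puts the week-6 items into one appointment: "All patients will return to the clinic for 1-week and 6-week post-surgery follow up appointments and will fill out an NRS pain assessment". The PFDI, the POP-Q examination and the complication review follow in the same sentence. The Calendar of Events adds the PFIQ-7 at week 6. Data Collection & Management is consistent with this: "Data collection will occur in the clinic and in the hospital at each encounter outlined in the Calendar of Events".

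A remote route is described once, for week 1. Patients are to be "called at home to remind them to fill out the week 1 questionnaire", and of that form the protocol says: "This questionnaire will be accompanied with a pre-paid and pre-addressed envelope for the patient to use or, if desired". The alternative offered is to carry the completed week-1 form to the week-6 visit. No phone, mail or electronic route is given for week 6.

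The Power Calculation section allows for losses: "Assuming a 15% loss to follow-up or drop-out rate for the duration of the study". The primary analysis is an independent t-test on NRS means. No method for missing scores and no analysis set is stated.

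**The concern.** The NRS is a short self-rating, PFDI-20 and PFIQ-7 are questionnaires, and a complication review can be done by conversation. Of the week-6 items, only the POP-Q needs the patient in the room. Followed as written, the plan gives up the other items whenever the visit is missed, even if the patient would answer a call.

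Attendance may be related to pain. A patient may stay away because she feels well, or because she has sought care elsewhere. If that relation differs by device, a t-test on attenders gives a biased week-6 comparison.

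Week 1 can be affected too. A patient who relies on carrying the week-1 form to week 6 and then does not come also loses her week-1 NRS and her opioid answers, which are on that form. Whether this can happen depends on which description of week 1 applies, because the protocol also describes a 1-week clinic appointment with an NRS.

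**Working it through.** **Inputs from the protocol.** Difference 2.5, SD 2.9, two-sided 5%, normal approximation, 21 evaluable and 24 enrolled per group, 15% loss (Power Calculation). Six-week pain rate 15-16% (opening summary and Background); 15.3-26.9% at weeks 4-6 with Capio Slim (Appendix 1).

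**Assumptions, not in the documents.** Mean NRS of 5 among patients with pain at week 6 and 0 otherwise; a gap of 1, 2 or 3 points between non-attenders and attenders; the whole 15% falling at week 6.

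**1. The plan's own size.** n per group = 2 × [2.9 × (1.960 + 0.842) / 2.5]² = 21.1, against 21 stated. Power at 21 is 79.8%, against at least 80% stated. For losses, 21 × 1.15 = 24.15, which matches the stated 24 (dividing by 0.85 gives 24.7). The stated figures reproduce closely.

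**2. Patients at stake.** 0.15 × 24 = 3.6 per arm, leaving 20.4. This is a ceiling. For comparison, the expected number in pain per arm is 0.15 × 24 = 3.6 to 0.16 × 24 = 3.8 at the headline rate, and 0.153 × 24 = 3.7 to 0.269 × 24 = 6.5 on Appendix 1. At the ceiling, about as many patients are unobserved as the headline rate expects to have pain.

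**3. Bias.** Let m be the fraction missing and g the non-attender minus attender gap. The full-arm mean is (1 − m) × A + m × (A + g) = A + m × g, where A is the attenders' mean. The attenders' mean is therefore off by m × g.

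| Gap, one arm only | 15% missing | 7.5% missing (half recovered at random) |
|---|---|---|
| 1 point | 0.15 | 0.075 |
| 2 points | 0.30 | 0.15 |
| 3 points | 0.45 | 0.225 |

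Equal gaps in both arms cancel. Gaps in opposite directions double the figures.

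**4. Scale for comparison.** Assumed arm mean at week 6: 0.15 × 5 = 0.75, up to 0.269 × 5 = 1.35.

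**5. Precision.** Power = Φ[2.5 / (2.9 × √(2/n)) − 1.960]. With n = 20.4 it is 78.6%; with n = 22.2 (half recovered) 81.9%; with n = 24 it is 84.8%. These use the plan's difference and its day-1 SD, so they show the effect of lost numbers only and are not a forecast of week-6 power.

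**The case against.** Several points on the other side stand, and they limit the size of the problem.

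- **The 15% is not a week-6 non-attendance rate.** A reader might infer that 15% of patients will miss week 6 and could all be phoned. The protocol's figure covers loss or drop-out of any kind over the whole study. It may include withdrawals and, since consent precedes surgery and randomization happens in the operating room, losses before surgery. A call recovers neither.
- **The harms record is not lost.** A reader might infer that non-attenders drop out of the safety data. Adverse events are also scheduled intraoperatively, on day 1 and at week 1. Readmissions, emergency room evaluations, unplanned visits and reoperations are reportable. What is lost is the scheduled week-6 review.
- **The formal decision is little exposed.** The rejection rule in the Power Calculation section refers to immediate postoperative pain, and the day-1 form is given on morning rounds.
- **Retention measures exist.** Eligibility requires acceptance of the 6-week visit and willingness to complete the questionnaires, and a gift card is scheduled at week 6. These encourage attendance but collect nothing from a patient who does not come.
- **The in-person wording is loose.** The protocol contradicts it for week 1, so it may not be meant as a strict bar at week 6. Even so, no other week-6 route is written anywhere.
- **The bias is hypothetical.** At a 2-point gap it is 0.30, or 12% of the 2.5-point threshold. That yardstick is generous at week 6, however, because 2.5 exceeds the whole assumed arm mean.
- **Enrolment was already raised for losses**, from 42 to 48, so the cost in power is modest. Higher enrolment does not address selection.

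**Conclusion.** The point holds as a cheap improvement to data collection at a named primary timepoint. As written, a patient who misses week 6 but would still answer loses her week-6 NRS, PFDI-20/PFIQ-7 and complication review, and possibly her week-1 NRS and opioid answers. At most about 3.6 of 24 patients per arm are affected. Under the assumed gaps of 1 to 3 points in one arm, with the full 15% missing, the bias in the week-6 difference is 0.15 to 0.45 points, against an assumed arm mean of about 0.75 to 1.35. The loss in power at the plan's effect size is from 84.8% to 78.6%, most of which the enrolment allowance already anticipates.

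The documents do not show that attendance depends on pain or device, so they do not support a claim that the week-6 result will be biased. They also do not support a claim that the day-1 comparison or the trial's rejection rule is compromised.

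**What to change.** In Post-Intervention Assessments and Clinical outcomes, extend the existing call and mail route to any patient who misses the week-6 visit and has not withdrawn consent to contact:

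- masked study staff phone her within a window set in advance (for example ±7 days) for the NRS items and the complication review;
- PFDI-20 and PFIQ-7 are sent with a pre-paid envelope;
- date and mode of collection are recorded, and the scores are included in the week-6 analysis.

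Of the items above and the POP-Q, only the POP-Q is then necessarily missing for a patient who responds. In the same edit, reconcile the statements on week 1: Clinical outcomes has the form collected in person, while Post-Intervention Assessments describes both a mailed or carried form and a 1-week clinic appointment.

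The cost is protocol wording and at most about 3 to 4 short calls per arm by existing staff. The downside is a few scores collected by a different mode; because mode is recorded, the analysis can be repeated without them.

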To conduct a prospective, randomized, single-blind trial of sacrospinous ligament fixation of the cervix or vaginal apex using Anchorsure® system versus the CapioTM Slim device in women with \geq Stage II pelvic organ prolapse who are undergoing native tissue vaginal repair. The **primary outcome** will be the level of postoperative pain using a 10-point numerical rating scale (NRS) on postoperative day 1, week 1, and 6 weeks postoperatively for pain that is localized to the posterior thigh or buttocks on the side(s) that the sacrospinous fixation was performed. The difference in mean pain ratings will be at least 2.5 on the 10-point NRS.

Hypothesis 2: Surgeon satisfaction, surgical efficiency, intraoperative complications, objective surgical success, symptomatic success, opioid use within the first week postoperatively following hospitalization, and overall postoperative pelvic pain will be similar for both devices.

Specific Aim 2:

The **secondary outcomes** will compare overall surgeon satisfaction with the 2 devices using a 5-point Likert rating scale and surgical efficiency measured in minutes from the start of the use of the surgical device until the surgeon is satisfied with the application of all sacrospinous sutures (does not require the sutures to be tied down). Intraoperative complication related to sacrospinous ligament suspension will be recorded including the need for suture or anchor replacement, hemorrhage that requires additional surgical interventions or blood transfusion, and equipment malfunction. General postoperative pelvic pain will be assessed at postoperative day 1, week 1, and 6 weeks along with buttock and posterior thigh pain via NRS questionnaires. Objective apical repair anatomical success will be assessed at the 6 week postoperative visit via a POP-Q examination with Stage II or greater indicating anatomical failure. Symptomatic surgical success will be evaluated by statistically significant increases or decreases in the responses to the PFDI-20 and PFIQ-7 questionnaires at the 6 week postoperative values.

SUBJECT SELECTION

Inclusion Criteria

- 1. Female patients
- 2. At least 21 years of age
- 3. Surgical plan that includes a native tissue vaginal repair with apical support via sacrospinous ligament fixation. We will permit both hysteropexy and post-hysterectomy sacrospinous ligament suspension
- 4. Understanding and acceptance of the need to return for the 6 week followup visit

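### The paired pre/post t-tests planned for PFDI and PFIQ do not compare the two devices, so they cannot address the symptomatic-success part of Hypothesis 2

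*Combined protocol and SAP*

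**What the plan says.** Hypothesis 2 (Study Objectives) is a statement about the two devices. It predicts that "symptomatic success, opioid use within the first week postoperatively following hospitalization, and overall postoperative pelvic pain will be similar for both devices". The Clinical outcomes section likewise introduces the secondary measures, symptomatic success among them, as showing how far the study intervention influences each one.

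The operational definitions look elsewhere. Specific Aim 2 says: "Symptomatic surgical success will be evaluated by statistically significant increases or decreases in the responses to the PFDI-20 and PFIQ-7 questionnaires". Clinical outcomes says: "Symptomatic success will be assessed by the PDFI-20 guestionnaires to be given at 6-weeks post-operation and compared to preoperative values". The test sentence at the end of that section makes independent t-tests the default for continuous data, "except for the PFDI and PFIQ data that will use paired t-tests as the two samples are dependent".

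The sections also disagree on the instrument:

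- Pre-Intervention Assessments lists "9. PFDI questionnaire" and no PFIQ.
- Post-Intervention Assessments lists "PFDI questionnaire (6-week), physical examination including POP-Q (6-week", again with no PFIQ.
- The Calendar of Events has a row for "PFDI-20 and PFIQ-7 Forms", marked preoperatively and at week 6.
- Specific Aim 2 and the test sentence include the PFIQ, while the Clinical outcomes definition of symptomatic success names only the 20-item PFDI.

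**The concern.** The question is between arms and the planned test is within patients. A paired t-test of 6-week against preoperative scores shows whether women improved after prolapse surgery. It does not show whether one device did better than the other, so it makes no use of the randomised comparison.

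The practical risk lies in what happens at analysis. If the test is run in each arm, the natural step is to read the two p-values side by side. They can agree when the devices differ and disagree when they do not, because each depends on that arm's own mean change, variability and number of patients. If the test is pooled over arms, it says nothing about the devices. Under either reading, a statement in the report about symptomatic success by device would not rest on a valid comparison.

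**Working it through.** **1. Which samples are dependent?** The device arms are independent randomised groups. The only dependent samples are the same woman's two scores, and the Clinical outcomes definition confirms a comparison with preoperative values.

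**2. Is there a route back to a device contrast?**

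- The independent t-test is ruled out by an explicit exception.
- The chi-square test needs a per-patient success status. Specific Aim 2 defines success by statistical significance of a change, which belongs to a group, has no stated direction and makes no reference to arm.
- No section gives a change-score comparison, an ANCOVA or a responder definition for these scores.

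Steps 1 and 2 establish the defect. The rest only illustrates its size.

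**3. Inputs.** The plan gives no PFDI or PFIQ figure to reproduce. From Power Calculation: 24 enrolled per group, 15% loss, two-sided 5%. Evaluable n per arm = 24 × 0.85 = 20.4, taken as 20. The plan's own evaluable target, set for the pain score, is 21. Assumptions: normal change scores with SD 1 in each arm, and paired tests run per arm.

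**4. Formulas.**

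- Paired test in one arm with true mean change d: noncentral t with n − 1 df and noncentrality d√n. Call its power p.
- Between-arm t-test on change with true difference δ: noncentral t with 2n − 2 df and noncentrality δ√(n/2).
- Equal devices, exactly one arm significant: 2p(1 − p).

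**5. Devices differ, n = 20.**

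| True changes (SD) | Both paired tests significant | Between-arm power |
|---|---|---|
| 1.8 and 0.9 | 0.968 | 0.792 |
| 1.2 and 0.6 | 0.720 | 0.456 |

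In the first row δ = 0.9 and the noncentrality is 0.9 × √10 = 2.85.

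**6. Devices equal, n = 20.**

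| Common change (SD) | p per arm | Exactly one arm significant |
|---|---|---|
| 0.3 | 0.247 | 0.372 |
| 0.45 | 0.480 | 0.499 |
| 0.6 | 0.721 | 0.402 |
| 0.8 | 0.924 | 0.141 |
| 0.9 | 0.968 | 0.062 |
| 1.2 | 0.999 | 0.002 |

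A between-arm test rejects in 5% at every row. In the 0.6 SD row, 2 × 0.721 × 0.279 = 0.402.

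**7. Sensitivity to n.** At 0.6 SD the discordance is 0.381 with 21 per arm and 0.316 with 24. For 1.8 against 0.9 SD, 21 per arm gives 0.975 for both arms significant and 0.812 for between-arm power.

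**8. Precision of the right comparison.** The unadjusted 95% CI half-width is t(0.975, 2n − 2) × √(2/n). With n = 20 this is 2.024 × 0.316 = 0.640 SD of change. It is 0.624 at 21 and 0.581 at 24.

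**The case against.** The strongest objection is that the percentages describe a procedure the plan never states. It does not say that per-arm p-values will be computed or compared, and on a pooled reading none of those figures applies. With no SD or expected change in the documents, the discordance rate can lie anywhere from 50% to 0.2%, and the first masking example assumes a device difference where the hypothesis expects none. This stands: the figures are illustrations and should carry no weight beyond that. It does not rescue the plan, since the pooled reading contains no device contrast at all.

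Using 20 per arm rather than the planned 21 is a fair criticism, but step 7 shows that it changes little.

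The PFIQ-7 disagreement may be editorial. Data Collection & Management ties collection to the encounters in the calendar, which schedules both forms, so the shorter lists can be read as abbreviations. That is reasonable, and the point is minor, but the sections should still agree.

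The caution about concluding similarity applies to every outcome in Hypothesis 2, and ANCOVA rather than a t-test on change is a matter of efficiency. Both points are right.

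Finally, this is one of several secondary outcomes, the sample size was set for pain, and a biostatistics department will collaborate on the analysis. That limits the consequence. It does not supply the missing comparison, because the section names a specific test and that test is the wrong one for the question.

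**Conclusion.** The concern holds. As written, the analysis of PFDI and PFIQ cannot answer the device question that Hypothesis 2 poses, and this follows from the text alone.

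Under the stated assumptions, misleading discordance between arms matters mainly when the common change is below about 0.8 SD. Masking of a real device difference matters mainly when both changes are large. Where this trial would fall is unknown, because the documents give no figures for these scores.

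The matter is confined to a secondary outcome. The primary pain comparison already uses an independent t-test and is untouched. It should be fixed before analysis, so that the choice of test is not made after the data are seen.

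**What to change.** - **Clinical outcomes:** replace the paired t-tests for PFDI and PFIQ with a between-arm analysis. Preferred is ANCOVA of the 6-week score on arm, adjusted for the preoperative score. The acceptable minimum is an independent t-test on change, in line with the plan's default. Report the between-arm difference with its 95% CI, and keep within-arm change as description only.
- **Specific Aim 2:** reword symptomatic success to match, so that it no longer rests on a significant change in either direction.
- **Interpretation:** do not take a non-significant result as evidence that the devices are similar; the interval width in step 8 shows how much difference would remain compatible with the data.
- **Instruments:** reconcile the two assessment lists and the Clinical outcomes definition with Specific Aim 2 and the Calendar of Events on whether PFIQ-7 is collected and analysed.

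The cost is wording only. No extra patients or visits are needed, and no new data if the calendar is followed. If the two assessment lists were followed instead, PFIQ-7 would not be available.
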